#### Pre-intervention Tasks

Upon completing the informed consent portion, vitals will be collected. Heart rate (HR) and blood pressure (BP) will be measured. Participant will complete the following surveys, A pain numerical rating scale (NRS) and the Pain Catastrophizing Scale (PCS) will all be used to evaluate the participants' pain levels and their perceptions of pain. The Brief Pain Inventory-Short Form and the Fibromyalgia Impact Questionnaire both assess the influences pain has on their lives. Psychosocial factors will be measured using the Positive and Negative Affect Scale (PANAS) and the PROMIS Emotional Distress Short Form for anxiety, depression, and anger.

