### SPECIFIC AIMS

1. The purpose of this project is to evaluate the feasibility and effectiveness of VR as a treatment option for older adults with chronic osteoarthritic knee pain.
2. Aim 1: Implement a pilot study and collect data on the feasibility of VR and its effects on pain for older adults with chronic osteoarthritic knee pain.
3. Aim 2: Analyze the feasibility of VR for this population, including looking at simulation sickness factors and drop out reasons/rates, and its impact on chronic pain immediately prior to and immediately post intervention, as well as a few days post intervention.
4. Sub-study Aim 1: The aim of this sub-study is to compare the effectiveness of a virtual reality meditation session and a non-immersive meditation session for improving pain, affect, and physiological vital stats in adults with fibromyalgia.
5. Sub-study Aim 2: We hypothesize that the VR meditation session will facilitate greater improvements in pain, affect, and physiological vital stats as compared to the non-immersive meditation intervention.

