### **Sub-study:**

#### Inclusion Criteria:

1. Adults ages 18 and older (no upper limit)
2. Diagnosis of fibromyalgia with a minimum baseline pain level of 3 on an NPRS
3. English-speaking
4. Willing and able to visit the Brigham and Women's Pain Management Center site on two separate occasions to participate in the sub-study

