#### Quantitative Sensory Testing (QST):

QST measurements will include pressure pain sensitivity assessed using an analog algometer with a 1-cm^2 rubber probe (FPK20, Wagner Instruments, Greenwich, CT, USA)

to quantify pressure pain thresholds (PPT) on the bilateral trapezius muscles and temporal summation in triplicate using a 40 g Neuroopen Neurotip (Owen Mumford, Oxfordshire, United Kingdom) a train of 10 identical stimuli (1 Hz) using a metronome for timing.

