#### Post-Intervention Surveys

Immediately following completion of the meditation sessions, vital signs will be taken for a second time (HR and BP). QST will then be performed for a second time. Three surveys will relate to the VR or non-immersive meditation experiences, the User Engagement Scale (UES), the Simulator Sickness Questionnaire (SSQ), and the Meditation Experience Questionnaire (MEQ). The participant will conclude by completing two questionnaires which are identical to some of the pre-intervention ones. Those are the pain numerical rating scale (NRS) and the PANAS.

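### Sub-study baseline heart rate and blood pressure are taken on completing consent, before the surveys and pain testing, so the pre-to-post change is not specific to the meditation and its starting point is undefined at the second visit

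*Protocol*

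**What the plan says.** The protocol's Specific Aims make vital signs an outcome of the sub-study. The aim is to compare the two sessions for "improving pain, affect, and physiological vital stats in adults with fibromyalgia", and the hypothesis is directional: "We hypothesize that the VR meditation session will facilitate greater improvements in pain, affect, and physiological vital stats" than the non-immersive session. The inclusion criteria require attendance at the "site on two separate occasions to participate in the sub-study", so each participant is seen twice.

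Pre-intervention Tasks sets the baseline: "Upon completing the informed consent portion, vitals will be collected". The questionnaires come next, beginning "Participant will complete the following surveys, A pain numerical rating scale (NRS) and the Pain Catastrophizing Scale (PCS". The section names six instruments: the pain NRS, PCS, BPI-SF, Fibromyalgia Impact Questionnaire, PANAS and PROMIS short forms. The QST section follows, with pressure pain thresholds on both trapezius muscles and "temporal summation in triplicate using a 40 g Neuroopen Neurotip". The session itself lasts 10 to 20 minutes in either format.

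Post-Intervention Surveys sets the second reading: "Immediately following completion of the meditation sessions, vital signs will be taken for a second time (HR and BP". After that, "QST will then be performed for a second time".

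**The concern.** A change score measures what happens between its two readings. Here the second reading sits right against the meditation, but the first is separated from it by a block of questionnaires and a painful procedure. A fall in HR or BP within a visit could be credited to meditation when part of it reflects sitting quietly after consent. Equally, a response to QST could mask a real fall.

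The only stated anchor for the baseline is completion of consent, which would normally happen once. One description of the pre-intervention tasks serves both visits, and it does not say what the reading is timed from at the second. The comparison of the two sessions relies on the pre-session part of each visit being alike, and the protocol does not secure that for HR and BP.

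**Working it through.** The protocol gives no standard deviation, effect size or power for HR or BP, so there is no stated figure to reproduce. The check is of the order of procedures, followed by simple algebra.

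**Order of steps within a visit, as the sections run**

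1. Consent completed, then HR and BP (Pre-intervention Tasks).
2. Six questionnaires (same section).
3. First QST (Quantitative Sensory Testing). Its place before the session is inferred from the order of sections and from the later QST being described as the second.
4. VR or non-immersive meditation, 10 to 20 minutes (Virtual Task; Non-Immersive Meditation).
5. HR and BP again, immediately (Post-Intervention Surveys).
6. Second QST, then the remaining questionnaires.

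The interval between the two readings holds steps 2, 3 and 4. Only step 4 is the intervention.

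**Share of the interval taken by meditation**

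The sub-study states no survey time. As an assumption, take the main study's 10 to 20 minutes (Baseline Surveys).

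- Share = session / (session + surveys).
- Lowest: 10 / (10 + 20) = 33%.
- Highest: 20 / (20 + 10) = 67%.

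QST time is not stated; adding it lowers both figures.

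**What cancels in the contrast and what does not**

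For one participant, write

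- change at a visit = session effect + c + d (d at visit 1 only),

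where c is drift common to both visits (surveys, QST response, ordinary settling) and d is any settling specific to visit 1.

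- VR first: VR change minus non-immersive change = true difference + (c + d) - c = true difference + d.
- Non-immersive first: true difference + c - (c + d) = true difference - d.

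So c drops out and d does not. Averaged over N participants,

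- bias = d × (number VR first - number non-immersive first) / N.

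With N = 25 (Research Design and Methods):

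| Session order | Calculation | Absolute bias in the contrast |
|---|---|---|
| Split 13/12 | d × (13 - 12) / 25 | 0.04d |
| All the same session first | d × 25 / 25 | 1.00d |

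Under the 13/12 split the group bias is small, but each participant's difference is still shifted by +d or -d. Without adjustment for visit, this adds d² × (1 - 0.04²) = 0.998d² to the variance of the paired differences. Adjusting for visit removes the average d, but not its variation between people.

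The documents give neither d nor the session order, so the result stays as a multiple of d. The sign of d is also open.

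**The case against.** The strongest reply is that the hypothesis compares two sessions. If both visits follow the same sequence, survey time, QST response and shared settling cancel. That stands, and it is why the point is minor.

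A reader might go further and infer that visit 1 is not comparable with visit 2. The protocol does not support that. It nowhere says that vital signs are timed differently at the second visit; it only leaves the timing point undefined there. The session order needed to turn d into a material bias is likewise not stated, and its absence is a separate matter.

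A reader might also infer that improvement is inflated in both sessions whatever happens. That is not supported either. Settling would exaggerate a fall, but a residual rise after painful testing would work against it. Consent Procedures gives participants ample time to decide, so some settling may already have occurred before the first reading at visit 1. No figure in mmHg can be drawn from the documents.

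Finally, the written order has some logic: vital signs come before QST both before and after the session, so neither reading directly follows pain testing. That is a fair reason for the present layout. It does not bring the first reading close to the session, and a rest after QST would serve the same purpose. Posture and device may sit in a procedures manual, but the order of steps is set in the protocol, and no analysis can recover a reading that was never taken directly before the session.

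**Conclusion.** The point holds in limited form, at minor severity. The within-visit change in HR or BP is not specific to the meditation, and the net direction of the error is unknown. On the assumed survey time, meditation fills between one third and two thirds of the interval, and less once QST is counted. For the between-session contrast, common drift cancels. A visit-1-only term would mostly add noise under a balanced order (bias 0.04d at 13/12) and would bias the contrast by up to 1.00d under a fixed order.

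This rests on reading the sections as the order of procedures, on consent being completed only at the first visit, and on d being non-zero. Only HR and BP are affected; pain and affect have their own baselines.

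**What to change.** At both visits, take the pre-session HR and BP at one defined point: after the surveys and QST, following a short seated rest, and immediately before the meditation starts. Use the same posture and device as for the post-session reading, and word the step so that it does not depend on consent.

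Keep the surveys before QST. Moving QST ahead of them would put the baseline NRS and PANAS after painful stimulation and so alter the baseline of the pain and affect outcomes.

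The cost is a few minutes of rest per visit. An existing measurement is moved and none is added.

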#### Quantitative Sensory Testing (QST):

QST measurements will include pressure pain sensitivity assessed using an analog algometer with a 1-cm^2 rubber probe (FPK20, Wagner Instruments, Greenwich, CT, USA)

to quantify pressure pain thresholds (PPT) on the bilateral trapezius muscles and temporal summation in triplicate using a 40 g Neuroopen Neurotip (Owen Mumford, Oxfordshire, United Kingdom) a train of 10 identical stimuli (1 Hz) using a metronome for timing.

#### Virtual Task

Participants will engage and follow along with a 10-20 minute guided meditation through the VR. The meditation program may include simulated movement, relaxing music, and the voice of a meditation guide. The research team member will supervise the session, ensuring safety of the subject is maintained.

#### Non-Immersive Meditation

For this session, participants will be seated facing a screen which will display the meditation imagery. They will engage and follow along with a 10-20 minute guided meditation. The meditation program will include relaxing visuals and music, and the voice of a guide.

#### Post-Intervention Surveys

Immediately following completion of the meditation sessions, vital signs will be taken for a second time (HR and BP). QST will then be performed for a second time. Three surveys will relate to the VR or non-immersive meditation experiences, the User Engagement Scale (UES), the Simulator Sickness Questionnaire (SSQ), and the Meditation Experience Questionnaire (MEQ). The participant will conclude by completing two questionnaires which are identical to some of the pre-intervention ones. Those are the pain numerical rating scale (NRS) and the PANAS.

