## RESEARCH DESIGN AND METHODS

We will recruit 25 older adults with knee osteoarthritis from Brigham and Women's Hospital (BWH) to obtain 20 subjects with complete data collection. The sub-study will enroll 25 adults with fibromyalgia from BWH.

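### Fibromyalgia sub-study: the post-session pain NRS and PANAS are collected last, after the second pain-evoking QST, rather than directly after the session

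*Protocol*

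**What the plan says.** Sub-study Aim 2 (Protocol, Specific Aims) hypothesises that "the VR meditation session will facilitate greater improvements in pain, affect, and physiological vital stats as compared to the non-immersive meditation intervention".

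The sub-study's Post-Intervention Surveys section sets the order after each session:

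1. Heart rate and blood pressure, immediately after the meditation.
2. QST: "QST will then be performed for a second time".
3. Experience questionnaires (UES, SSQ, MEQ), listed next: "Three surveys will relate to the VR or non-immersive meditation experiences".
4. Pain NRS and PANAS: "The participant will conclude by completing two questionnaires which are identical to some of the pre-intervention ones".

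The Quantitative Sensory Testing section defines QST as pressure pain thresholds on both trapezius muscles plus temporal summation, done three times with a train of 10 pinprick stimuli. The sub-study background describes fibromyalgia patients as having lowered pain thresholds.

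Before the session, NRS and PANAS appear under Pre-intervention Tasks and QST in the section that follows. No wording states that one precedes the other. The sub-study inclusion criteria require attendance "on two separate occasions to participate in the sub-study", so the comparison reads as within-person. On size: "The sub-study will enroll 25 adults with fibromyalgia from BWH".

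**The concern.** Of the three hypothesis outcomes, only the vital signs are taken straight after the session. Pain and affect are rated after noxious testing in a group selected for pain sensitivity, and, by order of listing, after three further questionnaires. If QST leaves some residual soreness or irritation, the final NRS and PANAS would carry it. No rating falls between the end of the session and QST, so such an after-effect could not be separated directly. Relating QST response to the later ratings would be only an indirect check.

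Three things could follow:

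- Each session's pre-post change would include any after-effect.
- The contrast between sessions would lose precision if the after-effect varies within a person from one visit to the other.
- A short-lived benefit could have partly faded by the time it is rated.

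**Working it through.** **Order of assessments.** The words that place QST next after the vital signs, and those that have the participant conclude with NRS and PANAS, fix both ratings after QST. The position of UES, SSQ and MEQ rests on listing order. No other section supplies a rating between the session and the second QST, and no rest interval after QST is stated.

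**Effect on the VR-versus-screen contrast.** The protocol gives no power, effect size or SD for the sub-study, so there is no figure to reproduce. The only input from the document is n = 25 (Research Design and Methods). The assumed inputs are:

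- true VR advantage D = 1.0 NRS point;
- SD of the paired difference 2.0, or 2.5 as an alternative;
- after-effect with SD s per session, correlation rho between a person's two sessions, and independent of the rest of the paired difference;
- two-sided alpha 0.05, paired t test.

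Formulas: SD_new = sqrt(SD² + 2·s²·(1 − rho)); noncentrality = D·sqrt(25)/SD_new on 24 degrees of freedom; equivalent sample inflation = SD_new²/SD² − 1.

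Worked case, SD 2.0, s = 1.0, rho = 0: SD_new = sqrt(4 + 2) = 2.449, noncentrality = 5/2.449 = 2.04, power 0.500, inflation 6/4 − 1 = 50%.

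With no after-effect, power is 0.670 at SD 2.0 and 0.484 at SD 2.5. With one:

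| s | rho | SD 2.0: SD_new | power | inflation | SD 2.5: SD_new | power | inflation |
|---|---|---|---|---|---|---|---|
| 0.5 | 0 | 2.121 | 0.619 | 12.5% | 2.598 | 0.455 | 8% |
| 0.5 | 0.5 | 2.062 | 0.643 | 6.25% | 2.550 | 0.469 | 4% |
| 0.5 | 0.8 | 2.025 | 0.659 | 2.5% | 2.520 | 0.478 | 1.6% |
| 1.0 | 0 | 2.449 | 0.500 | 50% | 2.872 | 0.387 | 32% |
| 1.0 | 0.5 | 2.236 | 0.574 | 25% | 2.693 | 0.430 | 16% |
| 1.0 | 0.8 | 2.098 | 0.628 | 10% | 2.579 | 0.461 | 6.4% |
| any | 1 | 2.000 | 0.670 | 0% | 2.500 | 0.484 | 0% |

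A smaller after-effect costs less: with s = 0.3 and SD 2.0, power is 0.651 at rho = 0 and 0.660 at rho = 0.5.

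The mean of the after-effect matters to the contrast only if it differs between sessions, and the protocol gives no reason to expect that.

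**Effect on the within-session pain change.** Assume an after-effect of 0.3 point that fades fully between the two QST rounds. Bias = (after-effect in the post rating) − (after-effect in the pre rating):

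| Pre NRS | Post NRS | Bias |
|---|---|---|
| before first QST | after second QST | 0.3 − 0 = +0.3 |
| after first QST | after second QST | 0.3 − 0.3 = 0 |
| after first QST | before second QST | 0 − 0.3 = −0.3 |
| before first QST | before second QST | 0 − 0 = 0 |

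The first two rows are the two possible readings of the current text. The third shows that moving only the post-session rating could create a bias.

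**Effect of delay alone.** Expected Benefits is firm about benefit only during the VR experience and calls hours or days afterwards possible. If 10% of the assumed advantage has faded by the time of rating (D = 0.9), power is 0.579 at SD 2.0 and 0.408 at SD 2.5. At 20% (D = 0.8) it is 0.484 and 0.336. A shared order does not cancel this loss. The fading fractions are assumptions; the protocol gives no rate.

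**The case against.** **Nothing in the text is false or contradictory.** The aim that speaks of ratings immediately after the intervention belongs to the knee osteoarthritis study, which has no QST. In the sub-study only the vital signs are promised immediately. This stands: the point is that the order is poorly chosen, not that the protocol breaks a commitment.

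**The mechanism is not demonstrated.** Lowered pain thresholds concern sensitivity to a stimulus, not how long it colours a later rating, and the intervening questionnaires may allow recovery. For PANAS there is no indication of size at all. This also stands, and it is why only a possible after-effect is claimed.

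**The aims are comparative and the order is common to both sessions.** An equal or stable after-effect cancels, so no bias in the contrast has been shown. This is correct and limits the point to precision, possible dilution and the within-session change.

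**The figures are illustrative.** The largest losses need an after-effect SD of 1.0 with no within-person stability. An SD of 0.3, in line with the 0.3-point mean used for the bias example, costs only 1 to 2 percentage points of power. This is fair; the range should be read from zero upward.

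**The present order can be defended.** QST is itself a pain-related measure, Aim 2 does not name an instrument for pain, and the present order obtains QST early. However, the aims do not name QST, whereas NRS and PANAS are the direct ratings of pain and affect repeated after the session. Giving them priority is the more natural choice.

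**Conclusion.** The point holds as a minor design weakness. The protocol explicitly places the post-session pain NRS and PANAS after the second QST, so two of the three hypothesis outcomes are not rated directly after the session and may carry a QST after-effect.

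The main VR-versus-screen contrast is largely protected. Under the assumptions shown, the loss of power from after-effect noise runs from nil (full within-person stability) to 0.17 (0.670 to 0.500, at SD 2.0, after-effect SD 1.0 and no stability). Fading of a short-lived benefit could add to it. Within-session change could be biased by the mean after-effect if the baseline rating precedes the first QST, which the protocol suggests by layout but does not state. Everything except n = 25 is assumed. The comparison is not invalidated.

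**What to change.** Collect the post-session NRS and PANAS right after the session, together with the vital signs and before the second QST. Then do QST, followed by UES, SSQ and MEQ. State explicitly that NRS and PANAS precede QST at both time points and in both sessions; changing the post-session order alone could introduce a bias if the baseline rating currently follows QST.

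The cost is a reordered visit checklist and REDCap form sequence. The second QST and the experience questionnaires would start a few minutes later, so a very brief effect on QST would be measured slightly later. The first QST round would still lie between the pre and post ratings, so some after-effect from that round may remain.

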## FORESEEABLE RISKS AND DISCOMFORTS

### Risks from VR:

Contact with objects: Participants' vision is occluded by the Virtual Reality (VR) headset. In general, they will perform the VR sitting, but the program may prompt them to move their arms and/or legs during the session.

Simulator Sickness: Some participants experience simulator sickness while in the VR experience particularly after prolonged exposure. Simulator sickness symptoms can include fatigue, headache, eye strain, difficulty focusing, increased saliva in mouth, sweating, or nausea. This risk is moderate. We have 3 methods to reduce this risk. 1) Dosage of VR for this study is between 10-20 minutes which has been reported as typically used in the literature, so risk for motion sickness is reduced. 2) Participants will complete the Simulator Sickness Questionnaire after each experience to monitor for motion sickness. 3) Participants can halt any VR at any time for any reason.

Seizures: Some people may experience severe dizziness, seizures, eye or muscle twitching or blackouts triggered by light flashes or patterns during the VR. This risk is quite small. We have 2 ways to reduce this risk: 1) People with a known risk for seizures

will be excluded from this study. 2) If a subject experiences any of these symptoms we will immediately stop the VR. We will provide any indicated immediate supportive care, we will recommend that they see a doctor, and they will be discontinued from the study.

VR headset may be uncomfortable: Some people may find wearing the headset uncomfortable. This risk is small. We have 2 methods to reduce this risk: 1) we will work with the participant to adjust the headset to be as comfortable as possible. 2) participants can stop the VR experience at any time for any reason.

Contamination: The VR headset is tightfitting and in close contact with the skin of the face. It is possible that participants may cross contaminate contagious skin or eye disorders. This risk is small. We have 2 methods to reduce this risk: 1) We will exclude people who have active, contagious skin or eye infections. 2) We will use a washable face protector for each visit. Each device will be wiped with antibacterial cleaners after each use.

Exposure to trigger in a VR experience: VR experiences can seem very real, and a participant may be exposed to an item or situation (e.g. heights) that can trigger an adverse reaction. This risk is small. We have 2 methods to reduce this risk. 1) There will be a variety of VR meditation experiences that participants can choose from so participants can pick experiences that appeal to them and do not appear to have any triggers. 2) Participants can halt any VR experience at any time for any reason.

